Conflict of Interest is defined as a situation in which financial (funds paid outside of a sponsored project agreement), non-financial or other personal considerations compromise, or have the appearance of compromising, an individual's professional judgment in proposing, conducting, supervising, or reporting research (i.e., consulting, speaking, or acting as a Sponsor or Board member, etc).

If you are unsure about a COI please select "yes" and complete the following section.

No

Supporting Attachments

Please include any support attachments. NYSPI Investigators must upload their ancillary checklist and all supporting approvals for the checklist, as well as the SRMP. If you are submitting an NHSR determination request, ancillary checklist and SRMP is not required.

Some items that may need to be attached include sample data collection sheets, Sponsor Brochure/Protocol

Must be a Word Doc

8016 Continuing review form	Annual Review Form
7091R (Evaluation protocol) consent form	Consent
IND amendment to add 8016	FDA Correspondence
IND ownership transfer correspondence 2023	FDA Correspondence
Grant application	Grant
8016 Ancillary Review Checklist and Attestation_CA.11.20.24 (1).pdf	Misc/Other
8016 Area Lead Approval	Misc/Other
8016 Greenlight letter	Misc/Other
8016 Safety Review outcome letter	Misc/Other
DMP approval	Misc/Other
FCOI	Misc/Other
Letter of support from inpatient unit	Misc/Other
7091R (Evaluation protocol) PSF	Protocol

Upload all currently approved forms, even if they are no longer in use (i.e. you are in data analysis)

This should include the last approved consent/assent forms, HIPAA docs, scripts, advertisements, SSRP, Location/Funding/Personnel Supplements, Letters of Support, etc.

8016_Ad_6.13.23_Final (1).pdf	Advertisement
Consent quiz	Consent
Consent Form	Consent
8016 updated HIPAA_3.7.23.pdf	HIPAA
AE Log	Authorization
PD Log	Misc/Other
Table 2 (referenced in procedures)	Misc/Other
(PSF_2024) Effects of Repeated High_Cannabidiol Cannabis Administration on Experimental Pain and.pdf	Protocol

Title: Repeated Cannabis Administration on Experimental Pain and Abuse Liability

NCT: 04576507

Document date: April 14, 2025

Statistical Analysis

Overview: All data analyses will be based on models using repeated measures analysis of variance (RM-ANOVA) analyzed as a function of cannabis condition (active vs. inactive) and day (Day 1-15), and sets of planned comparisons, calculated with SPSS or SUPERANOVA statistical packages. The planned comparisons are *a priori*, and designed to test the specific hypothesis for each aim. Tests of differences for all comparisons will be based on F-statistics with degrees of freedom corrected, depending on the observed within-subject correlation of the measures, using the method of Geiser and Greenhouse or Huynh and Feldt. Results will be considered statistically significant at $p < 0.05$, using 2-tailed tests. Distribution of demographic variables (ethnicity, age, sex) will be described in terms of means, standard deviations, proportions, and 95% confidence intervals, where appropriate.

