Cold Pressor Test: The CPT apparatus consists of two refrigerated circulators, filled with warm (36.5-37.5°C) and cold (3.5-4.5°C) water. At the beginning of the procedure, a research assistant (same gender as the participant) will read a script describing the procedure to the participant, as well as take their blood pressure and heart rate as a safety assessment and for baseline values. Participants will then insert their non-dominant hand into the warm water and remove it after 3 minutes; skin temperature of the thumb pad will be measured. Blood pressure and heart rate will be taken halfway through the 3-minute period in the warm water tank. Participants will then insert their hand in the cold water and will be instructed to report when they first experience pain (pain threshold) and remove their hand when the cold water can no longer be tolerated (pain tolerance). Maximum immersion time will be 3 minutes. Immediately after hand removal, blood pressure, heart rate, and skin temperature will be measured. Participants will then complete measures of CPT-induced discomfort (described below). Individuals who do not report pain and/or do not remove their hand within 3 minutes will be excluded. If at any point that vitals are taken systolic pressure is greater than or equal to 180, diastolic pressure is greater than or equal to 110 (each measure monitored and confirmed by a manual reading), in which either is sustained after a manual redo for more than 120 seconds, will result in suspending the CPT for that participant for that given day. If a single reading of systolic blood pressure is greater than 200, or a single reading of diastolic blood pressure is greater than 120 (each measure confirmed by a manual reading), or a confirmed heart rate greater than 160, the CPT session will be immediately suspended for the participant that given day. Additionally, for either parameter, the participant's vital signs will be assessed every thirty minutes until it stabilizes within normal range under the guidance of the study physician. In the event that vital signs are not stabilized, we will assess the participant as described in the Criteria for Early Discontinuation section.

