--The Cold Pressor Test (CPT) may induce a rise in blood pressure and/or heart rate. If this occurs (to standards described below), the CPT will immediately be stopped, and the participant will be withdrawn from the study if heart rate or blood pressure values exceed safe limits. Emergency medical equipment is available in our laboratory, which is in a hospital where a full medical emergency back-up team is constantly available. Participants will perform the cold pressor test during training, and if their heart rate exceeds 160, their systolic blood pressure exceeds 180, or their diastolic blood pressure exceeds 110, they will be discharged from the study by the Investigator. Vital signs will be taken before, during, and after the CPT assessment during training. During laboratory sessions, if systolic blood pressure of greater than 180 or a diastolic blood pressure greater than 110 (each measure confirmed by manual reading), in which either is sustained for more than 120 sec. is observed, the CPT for that participant will be suspended for that given day. In addition, a single reading of systolic blood pressure greater than 200, or a single reading of diastolic pressure greater than 120 (each measure confirmed by manual reading), or a confirmed heart rate of greater than 160, will result in suspending the CPT for that participant for that given day. If any of these parameters is exceeded, we will immediately confer with a staff internist to determine whether the episode of hypertension or tachycardia is resolving and can be followed up on an outpatient basis, or whether acute medical intervention is indicated. We will also continue to take that participant's vital signs every 30 minutes until the episode has resolved or until a staff internist determines that acute medical intervention is indicated. If these changes are observed on a second occasion, the CPT will not be administered again to that participant.

Please fill out this Drug Supplement for EACH drug. Once completed click "Repeat" at the bottom of the page to enter another drug. Once all drugs have been entered click "Next"

Please enter the name of the study drug.

Cannabis

Is the drug approved by the FDA?

No

Is the drug being used in accordance with labeling?

No

Does use of the drug meet the requirements for exemption from IND requirements?

No

Has an IND been issued by the FDA?

For more information on Sponsor-Investigator responsibilities, please refer to: [FDA Information](#)

Yes

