Provide the IND number.

36369

Name the person/entity that holds/is the Sponsor of the IND.

If the IND holder is an OMH investigator, please contact the IRB for information on responsibilities of Sponsor-Investigators.

[name].

Please attach any correspondence from the FDA with your submission.

IND Ownership Transfer to [name] 2023 FDA Correspondence

RWF IND 036369 updates_8016_9.26.22.pdf FDA Correspondence

rwf IND Form of Notice_8016.pdf FDA Correspondence

RWF IND_1571+PSF_add 8016_6.8.22.pdf FDA Correspondence

Subjects

Target Enrollment:

This refers to the target subjects enrollment, i.e., the number of subjects necessary to complete research objectives.

20

Total number of subjects requested to reach target enrollment:

This refers to the estimated number of subjects you must "over-enroll" to meet your target enrollment either by active screening or review of records for eligibility.

24

Please identify the groups of the study and how many subjects will be enrolled in each group.

Click "save" at the end of each row.

If you have multiple groups, please use the number (#) assigned to each group on the left of this table to indicate that group in the inclusion/exclusion criteria table (to specify which inclusion/exclusion criteria belong to which subject group).

Numbers here should equate to the number entered for Target Enrollment.

#	Subject Group	Subject Number
1	Healthy, non-treatment seeking heavy cannabis smokers	20

Please provide a justification for your sample size.

Power calculations were performed using G*Power, with the following assumptions: significance level of $\alpha = 0.05$, effect size (Cohen's d) of 0.7, and within-subjects correlations of 0.6 for repeated measures. Based on our residential laboratory studies in cannabis smokers, we estimate that 4 of the 24 participants may drop out. The large within-subject correlations (typically ranging from 0.60-0.95) between conditions (active cannabis vs. inactive cannabis) allow for sufficient statistical power with $n=20$ completers.

Inclusion & Exclusion:

Give detailed inclusion and exclusion criteria (per group, if you have multiple groups). Note that order does not indicate importance. Click **Save** at the end of each row to both save data and to add a new row. For the final row, click **Save** and leave the new row blank.

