Events that occur in research that may represent unanticipated problems involving risks to subjects or others should be promptly reported using the Event report form within 10 days of the investigator's or research staff member's learning of the event, except for these circumstances:

- 1. If the event is related to a fatality that is related to study participation or possibly related to study participation, the incident should be report to the IRB within two (2) business days of discovery of the event.**
- 2. Events resulting in temporary or permanent interruption of study activities by the investigator, sponsor, or DSMB (Data Safety and Monitoring Board) to avoid potential harm to subjects should be reported within IRB within two (2) business days.**

Incidental and Unexpected Findings

Incidental findings are observations of potential clinical significance unexpectedly discovered in research participants and unrelated to the purpose or variables of the study.

Describe the plan to address incidental findings and unexpected findings about individuals from screening to the end of the subject's participation in the research.

In cases where the subject could possibly benefit medically or otherwise from the information, state whether or not the results of screening, research participation, research tests, etc., will be shared with subjects or their primary care provider.

In cases where the participant could possibly benefit medically or otherwise from study screening or other information, the results of screening, research participation, research tests, etc., will be shared with subjects and/or their primary care provider upon consent from the participant.

Data Analysis and References

Statistical/Data Analysis Plan

List the statistical methods to be used to address the primary and secondary objectives, specific aims, and/or research hypotheses.

Explain how missing data and outliers will be handled in the analysis. The analysis plan should be consistent with the study objectives. Include any sub-group analysis (e.g., gender or age group). Specify statistical methods and variables for each analysis. Describe how confounding variables will be controlled in the data analysis.

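### RM-ANOVA is the only model, with no missing-data rule and no named days per fit, so a multi-day fit would discard participants with one missing day; the cost is conditional and usually modest

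*SAP*

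**What the plan says.** The SAP (Statistical Analysis, Overview) states that "All data analyses will be based on models using repeated measures analysis of variance (RM-ANOVA", with condition and day as factors, planned comparisons, and Greenhouse-Geisser or Huynh-Feldt correction. The protocol's Statistical/Data Analysis Plan has the same text. The form's own prompt in that section asks the investigator to "Explain how missing data and outliers will be handled in the analysis". Neither document answers it, and neither lists the days in each model.

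The protocol itself creates two kinds of missing data.

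- **Dropout.** The sample-size justification says "we estimate that 4 of the 24 participants may drop out" and rests power on 20 completers, with an effect size of 0.7 and "within-subjects correlations of 0.6 for repeated measures".
- **Lost CPT days.** Exceeding the vital-sign limits "will result in suspending the CPT for that participant for that given day" (Protocol, Cold Pressor Test). The CPT and QST-TTS section applies the same procedures on inpatient test days. The section on termination after pain-testing adverse events adds: "If these changes are observed on a second occasion, the CPT will not be administered again to that participant". The same section also says that "the participant will be withdrawn from the study if heart rate or blood pressure values exceed safe limits".

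**The concern.** A sphericity-corrected RM-ANOVA conventionally needs a complete row per participant over the days fitted. The documents do not state listwise deletion, but it follows from the named model when no other rule is written.

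Two groups are exposed. Dropouts can lose their valid days for every outcome. Participants with a suspended CPT day can lose all their CPT data, though not their QST-TTS, drug-effect or sleep data. Enrolling 24 to obtain 20 completers allows for the first group but leaves its data unused. It does not allow for completers who lose CPT days.

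The number retained also depends on an unstated choice. The tolerance comparisons (General Overview: Day 9 versus Day 1, Day 12 or 15 versus Day 9) can be fitted on two days, Aim 1 on four test days, and the overall model on seven. CPT loss is selected on blood-pressure or heart-rate response, and the protocol lists increased heart rate as a cannabis effect, so loss may differ by condition.

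**Working it through.** **Inputs.** From the protocol: d = 0.7, r = 0.6, two-sided alpha 0.05, 20 completers, 24 enrolled, and CPT on Days 1, 2, 5, 8, 9, 12 and 15. Assumed, because no rate is given: 1, 3 or 5% of CPT test days lost.

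**1. The plan's own figure.** dz = 0.7/√(2 × (1 − 0.6)) = 0.7/√0.8 = 0.783. Two-sided paired-t power (noncentral t, noncentrality dz × √n) is 0.913 at n = 20, 0.938 at 22 and 0.956 at 24. The protocol gives no numerical power target; 20 completers fits 90% on this reading. If 0.7 is read as dz, power at 20 is 0.844.

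**2. Lost CPT days, no dropout.** With independent losses at rate p, a participant is complete over m days with probability (1 − p)^m. For seven days: 0.99^7 = 0.932, 0.97^7 = 0.808, 0.95^7 = 0.698. Of 20, that keeps 18.6, 16.2 and 14.0 on average. Power is averaged over a binomial number kept, k, with k − 1 df (paired error) or (k − 1)(m − 1) df (pooled error, equal correlation):

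| Loss per day | 7-day, paired | 7-day, pooled | 4-day, paired | 2-day pairs |
|---|---|---|---|---|
| 0% | 0.913 | 0.935 | 0.913 | 0.913 |
| 1% | 0.889 | 0.916 | 0.900 | 0.906 |
| 3% | 0.831 | 0.871 | 0.869 | 0.892 |
| 5% | 0.762 | 0.815 | 0.835 | 0.877 |

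If the losses fall in about 20% of participants, each at five times the rate, seven-day deletion gives 0.892/0.860/0.841 (paired) or 0.918/0.893/0.879 (pooled).

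**3. All-data mixed model.** This was simulated with 2,500 trials per scenario (Monte Carlo SE about 0.006) on day-level values, using an unstructured between-day covariance and Kenward-Roger df. Day 9 versus Day 1 at 1/3/5% loss gave 0.916/0.894/0.888 (independent) and 0.898/0.899/0.875 (clustered). Two-day fits in the same simulation gave 0.913/0.892/0.874 and 0.900/0.893/0.865. The mixed model's largest gain over pairs is 0.014.

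**4. Dropouts alone** (24 enrolled, 4 assumed to leave evenly over Days 2–15):

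| Contrast | Completers | Available pairs | Mixed model |
|---|---|---|---|
| Day 2 vs 1 | 0.912 | 0.954 | 0.954 |
| Day 5 vs 1 | 0.920 | 0.954 | 0.954 |
| Day 8 vs 1 | 0.899 | 0.932 | 0.934 |
| Day 9 vs 1 | 0.920 | 0.941 | 0.945 |
| Day 15 vs 9 | 0.918 | 0.918 | 0.917 |

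**5. Why pooled error is not a safe remedy.** Suppose correlation decays at 0.915 per day, which gives a mean of 0.6 over the seven days. Day 9 versus Day 1 then has r = 0.915^8 = 0.491 and variance 2(1 − 0.491) = 1.018, or 1.27 times the pooled 0.80. Day 12 versus Day 9 has r = 0.915^3 = 0.766 and variance 0.468, or 0.59 times. At 5% loss, the simulated type I error of an equal-correlation mixed model was 0.080–0.086 for the first and 0.012 for the second. The unstructured model held 0.044–0.056 over six contrasts and converged in at least 98.9% of trials.

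**6. Bias, as an illustration.** If the four highest Day 2 responders leave before Day 5 and the true Day 2 minus Day 1 difference is 0.70, complete cases estimate 0.59. An all-data fit with known covariance estimates 0.70.

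**The case against.** The strongest reply is that the model need not change. A two-day RM-ANOVA is a paired test, the SAP's planned comparisons allow it, and on all available pairs it loses almost nothing. That stands: most of the benefit comes from naming the days and keeping every available pair. The mixed model adds little beyond that.

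A reader might infer that power will fall to 0.76. The documents do not support this. That figure needs the highest assumed rate, independent losses, seven-day deletion and a paired error term together. The blood-pressure and heart-rate exclusion example and the discharge rule at training both favour a low rate. A suspension part-way through a day may still leave a usable day value, which the calculations ignore.

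A reader might also infer a flat contradiction between suspension and withdrawal. The withdrawal sentence follows a pointer to standards given later in the section, and those can be read as discharge at training and suspension for the day in sessions. A consistent reading exists, but the wording leaves it open.

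Finally, a change made now comes after data collection, with day order fixed and only participant blinding described. Dating the change discloses that discretion but does not remove it.

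**Conclusion.** The point holds in a limited form and is worth fixing. The documents name one model, give no missing-data rule although the form asks for one, and leave the days per fit open, while the protocol builds in dropouts and suspended CPT days. A multi-day RM-ANOVA run in the conventional way would discard valid data.

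The size depends on assumed loss rates, on whether losses cluster, and on d = 0.7 with r = 0.6. It ranges from no gain, if no test day is missing, to a seven-day fit at 0.76 (paired error) or 0.82 (pooled error) against about 0.88 for available pairs. Pooled error is reliable only near sphericity. The gain from dropouts' data is confined to contrasts with Day 1 among those examined.

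Two further inferences are not supported: that the plan prescribes listwise deletion, and that CPT results will be biased. The documents do not show whether the vital-sign response that triggers suspension is related to CPT latency.

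**What to change.** 1. Use all available observations, including those of non-completers, for each planned comparison, and name the days in each fit.
2. For outcomes measured on test days, fit a REML mixed model to day-level post-smoking values. Treat day as categorical, use a between-day covariance that does not assume equal correlation, and use Kenward-Roger df. An unstructured seven-day matrix has 7 × 8/2 = 28 parameters, so name the fallback in advance: two-day paired contrasts on all available pairs. State whether Aim 1 compares pre- or post-smoking values.
3. Report the planned RM-ANOVA alongside, with the number of participants it retains.
4. Report lost and partial CPT days by participant, day, condition and reason.
5. Add a simple missing-not-at-random check that shifts missing CPT latencies, for example from −0.7 to +0.7 SD (the design's effect size). Keep values between 0 and 180 s, since "Maximum immersion time will be 3 minutes".
6. Reconcile the suspension and withdrawal wording, because each gives a different missing-data pattern.
7. The protocol says the study is in data analysis only, so date and label the change as made after data collection.

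The cost is SAP wording and modest extra analysis, with no new data. The downsides are a post-collection change and reliance on missing-at-random, which reduces bias but does not remove it.
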